5.0 STATISTICAL PLAN

5.1 Preliminary Sample size determination:

This study seeks to explore if local antibiotics are effective in reducing infection. Existing literature estimates the rate of infection after intramedullary nailing for open-tibia fracture at 6-21%, with higher rates seen in developing countries^{23,24}. Based on the previous randomized controlled trial conducted at MOI, the rate of deep infection in patients with open tibia fractures who do not receive local antibiotics during operative management was estimated to be 12%. For a relative risk reduction of 50% in the rate of deep surgical site infections, with an alpha (two-sided) of 0.05 and power of 0.80, the estimated sample size was 712 patients (356 per group). Assuming a loss to follow-up of 20%, the final sample size needed was determined to be 890 patients. Given the anticipated enrollment of 15 participants per month, enrollment would take approximately 5 years for a single center study. The study described herein is a pilot trial with a 1-year enrollment period to include 100 patients, approximately 10-20% of the necessary sample size for the definitive trial.

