5.2.2 Additional analyses

Supplemental analyses. These analyses are designed to provide additional insight and support for the primary analysis, and to assess whether or not the methodological choices we made had an undue effect on the results. In reporting, they will be sharply distinguished from the primary outcome, and will not be highlighted as central or determinative findings in reports, publications,

abstracts, posters or other communications.

Additional sensitivity analyses will be conducted based on the following variables as base- line covariates: Gustilo fracture type, lower extremity fracture, wound contamination, time from injury to first debridement, antiseptic wound dressing in the emergency department, method of fixation, wound closure at initial debridement, age, work-related injury, and employment status. Such analyses will be reported descriptively and with confidence intervals, but no significance P- values will be given. Conclusions based on such subgroups or adjustments will be considered hypothesis-generating, and will not form the basis for highlighting in reports or publications.

Fisher’s Exact Test. We will report the results of Fisher’s exact test on the 2×2 cross- tabulation of the reoperation binary outcome and the treatment assignment. This does not take into account observation time. This is an independent statistical procedure, and may yield statistically inconsistent results.[◦]

Risk difference. We will report the 95% confidence interval for the risk difference between the groups. Because this will be conducted by an independent regression (binomial regression with the identity link), these new findings may be statistically inconsistent with the main analysis. Thus, we will only report 95% confidence intervals, omitting P-values. The risk difference is interpretively important and may be useful in future meta-analytic studies.

Combined analysis. At the conclusion of both trials, an additional analysis will be conducted in which both data sets are combined into a single analysis. This analysis, bearing similarity to a meta-analysis of original data, will yield a combined effect estimate and confidence interval. deviation. No P-value will be reported. Thus, this secondary analysis does not constitute an additional risk for declaring significance and no multiple comparison adjustment is mandated.

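### The risk difference has no term for observation time and no rule for participants lost before 12 months, so its value depends on an unwritten coding choice

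*Combined protocol and SAP*

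**What the plan says.** Section 5.2.1 (Primary pre-specified analysis) takes fracture-related infection (FRI) as a binary outcome, records each person's time under observation T, and chooses a complementary log-log binomial model so that person-time can be used.

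Section 5.2.2 (Additional analyses) adds a risk difference between the groups, to be "conducted by an independent regression (binomial regression with the identity link), these new findings may be statistically inconsistent with the main analysis". For that reason it will carry a 95% interval and no P-value. The plan also says: "The risk difference is interpretively important and may be useful in future meta-analytic studies". No time term, offset or follow-up window is given for this model.

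The Statistical considerations paragraph of 5.2.2 accepts that an intention-to-treat analysis cannot be done where the primary outcome is missing. It offers an exploratory regression of missingness and observation time on four predictors, and treatment arm is not one of them. It gives no rule for coding a participant whose follow-up is incomplete.

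Section 5.1 sets the scale of the problem: "Assuming a loss to follow-up of 20%, the final sample size needed was determined to be 890 patients".

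**The concern.** A binomial regression on treatment alone returns the difference between two proportions. Each proportion needs a numerator and a denominator, and the plan does not say where a participant belongs who leaves at, say, six weeks without infection. There are three natural choices:

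- **Rule A:** count the participant as event-free.
- **Rule B:** keep everyone with an observed infection and everyone who completes 12 months, and drop the rest.
- **Rule C:** keep only those followed to 12 months, whatever happened before dropout.

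These rules give different answers, and the choice could be made after the data are seen. About one participant in five would be affected under the plan's own assumption. The risk difference is the absolute measure of effect that the plan specifies for FRI, and the plan expects meta-analyses to use it. Leaving out the P-value does not help if the interval is centred on the wrong value.

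**Working it through.** **Inputs from the documents.** Section 5.1 gives a control risk of 12%, a halving of that risk ("For a relative risk reduction of 50% in the rate of deep surgical site infections"), two-sided alpha 0.05, power 0.80 and 20% loss. Section 4.7.2 says that FRI diagnosis is likely to peak between 3 and 6 months.

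**The plan's own figure.** With p1 = 0.12, p2 = 0.06, mean 0.09 and a pooled variance under the null:

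n per arm = [1.960·√(2·0.09·0.91) + 0.842·√(0.12·0.88 + 0.06·0.94)]² / 0.06² = 355.9, so 356 per arm and 712 in total. Then 712 / 0.80 = 890. Both figures are reproduced. The true risk difference is 12 − 6 = 6.0 points.

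**Assumptions not in the documents.** Infections are shared 5/10/15/45/15/10% over the six visit intervals (0–2 weeks, 2–6 weeks, 6 weeks–3 months, 3–6, 6–9 and 9–12 months). Loss is unrelated to infection within arm. Loss L takes one of four patterns: all at baseline; all at the 6-week visit; one sixth at the end of each interval; all at the 6-month visit.

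**Formulas.** Let a be the fraction of true infections that are observed, that is, the sum over intervals of (infection share × fraction still followed). For true risk p:

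- Rule A: risk = p·a
- Rule B: risk = p·a / [p·a + (1 − p)(1 − L)]
- Rule C: risk = p(1 − L) / (1 − L) = p

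**Equal 20% loss, true difference 6.0 points.** For loss spread over visits, the fractions followed are 1, 1 − L/6, 1 − 2L/6 and so on, so a = 1 − L·(0.10·1 + 0.15·2 + 0.45·3 + 0.15·4 + 0.10·5)/6 = 1 − 0.475·L = 0.905.

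- Rule A: 0.905 × 6.0 = 5.4 points.
- Rule B, control: 0.1086 / (0.1086 + 0.704) = 13.36%. Gentamicin: 0.0543 / (0.0543 + 0.752) = 6.73%. The difference is 6.6 points.

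| Loss pattern | a | Rule A | Rule B | Rule C |
|---|---|---|---|---|
| Baseline | 1 − L = 0.80 | 4.8 | 6.0 | 6.0 |
| 6 weeks | 1 − 0.85·L = 0.83 | 5.0 | 6.2 | 6.0 |
| Spread over visits | 1 − 0.475·L = 0.905 | 5.4 | 6.6 | 6.0 |
| 6 months | 1 − 0.25·L = 0.95 | 5.7 | 6.9 | 6.0 |

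**No true effect (12% in both arms), loss 10% control v 30% gentamicin.** This split is an illustration. If the arms are swapped, benefit and harm swap too. Rule A gives a false benefit of 12 × (a at 10% − a at 30%) points. Rule B uses the same formula as above.

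| Loss pattern | Rule A: false benefit | Rule B: false harm |
|---|---|---|
| Baseline | 12 × (0.90 − 0.70) = 2.4 | 12.0 − 12.0 = 0 |
| 6 weeks | 12 × (0.915 − 0.745) = 2.0 | 12.7 − 12.2 = 0.5 |
| Spread over visits | 12 × (0.9525 − 0.8575) = 1.1 | 14.3 − 12.6 = 1.7 |
| 6 months | 12 × (0.975 − 0.925) = 0.6 | 15.3 − 12.9 = 2.4 |

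With equal loss in the two arms and no effect, both rules give zero.

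**Using T.** In each interval, the observed infections and the number at risk are both multiplied by the fraction still followed. The interval hazard is therefore unchanged, and the Kaplan-Meier product returns 12% and 6% in every pattern above.

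**Infection-related loss.** Suppose each arm loses 20% overall but a fraction q of its infected participants. Rule C then gives p(1 − q)/0.8. With q = 0.4 in control and 0.1 in gentamicin: 0.12·0.6/0.8 − 0.06·0.9/0.8 = 9.0 − 6.75 = 2.25 points. Reversed: 13.5 − 4.5 = 9.0 points. Kaplan-Meier does not in general remove this kind of bias.

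**Scale.** The 95% half-width is 1.96·√[(0.12·0.88 + 0.06·0.94)/n]. This is 4.2 points at 356 per arm and 12.5 points at 40 per arm (the pilot's 50 per arm after 20% loss).

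**The case against.** Several points on the other side stand.

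- **Bias is conditional.** A reader might infer that the assumed 20% loss by itself biases the risk difference. It does not. Rule C is unbiased when loss is unrelated to infection, Rule B is unbiased when all loss is at baseline, and both A and B are unbiased under no effect with equal, unrelated loss. The plan commits to none of these rules, so what is established is dependence on an unstated choice. Rule C also discards infections already seen in participants who later leave.
- **The identity link is not at fault.** With treatment as the only term it returns the crude difference in proportions. Any binomial model without a time term has the same gap.
- **The inconsistency remark is not an admission of bias.** It warns that separate procedures can disagree. A Kaplan-Meier difference could also disagree with the primary result. The sentence in 5.2.2 stating that observation time is not taken into account belongs to Fisher's test on reoperation. For the risk difference, it is an inference from the absence of any time term.
- **Unequal loss is not predicted.** Section 4.6 (Masking) masks participants, care providers and data collectors, which makes a 10% v 30% split under no effect hard to motivate.
- **Some mitigation exists.** Section 4.4 includes FRI questions by telephone before each visit from 6 weeks, so a missed visit need not mean unknown status. The telephone criteria are still being validated in the pilot (4.7.1, Feasibility Trial Outcomes).
- **The stakes are limited.** Section 5.2 describes these methods mainly for planning the definitive trial and expects the SAP to be revised. The analysis is supplemental, reported by interval only, and not to be presented as central.

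These points lower the weight of the concern but do not supply the missing rule. The planned revision of the SAP is a natural time to add it.

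**Conclusion.** The point holds in a conditional form. The risk difference has neither a time term nor a rule for incomplete follow-up, although T is recorded. Under equal 20% loss unrelated to infection, the coding choice alone places a true 6.0-point difference between about 4.8 and 6.9 points. Under the illustrative 10% v 30% loss, a null effect can appear as a benefit or harm of up to about 2 points. These sizes rest on assumed infection timing and loss patterns; only the 12%, 6%, 20% and the 3 to 6 month peak come from the documents.

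Against a half-width of 4.2 points at the definitive sample size, the equal-loss shifts (−1.2 to +0.9) are modest but not negligible. Against 12.5 points in the pilot they are minor. The documents do not support saying that the estimate will be biased, that the identity link causes it, or that the primary analysis or the sample size is affected by this point.

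**What to change.** In section 5.2.2, replace the crude identity-link estimate with the difference in 12-month FRI risks estimated using T. Either take each arm's risk from Kaplan-Meier with a Greenwood or bootstrap 95% interval, or derive both risks from an interval-based complementary log-log model with a bootstrap interval. If the second route is taken, the SAP must state the interval structure, because 5.2.1 says that person-time is used without saying how.

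Define T for a participant who is lost, including whether a telephone contact counts as follow-up. Add a sensitivity analysis that varies infection risk among the lost, separately by arm, because Kaplan-Meier does not remove infection-related loss. If the crude difference is kept as a contrast, state its coding rule in advance.

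The cost is SAP wording and a little more analysis of data already collected. The analysis stays supplemental and interval-only, and the 356 per group, 712 and 890 do not change.

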6.0 DATA MANAGEMENT

6.1 Case Report Forms and Data Transmission

Clinical sites will be provided with the trial case report forms (CRFs) prior to initiation of enrollment. Research personnel at each clinical site will submit the required data, as detailed on

the CRFs, using the Research Electronic Data Capture (REDCap) electronic data capture system. Clinical site personnel will receive a unique login and password.

6.2 Data Integrity

The REDCap system uses a variety of mechanisms for checking data at the time of entry including skip logic, range checks, and data type checks. Interim analyses will serve as a quality control method to assess missing, implausible, or inconsistent data.

7.0 ETHICS AND DISSEMINATION

7.1 Research Ethics Approval

Ethical approval for this trial was obtained from the National Institute of Medical Research, Tanzania (Ref#: NIMR/HQ/R.8a/Vol. IX/2958), and the UCSF Human Subjects Research Internal Review Board (IRB# 17-23950, Ref#: 260102).

The GO Tibia trial was registered at ClinicalTrials.gov (NCT03559400) on June 18, 2018 (<https://clinicaltrials.gov/ct2/show/NCT03559400>).

Any proposed protocol modifications will be submitted for approval to both ethical review boards.

7.2 Consent

If a patient is deemed eligible for the study, designated study personnel will obtain informed consent from the patient (preferred) or proxy as soon as feasibly possible. The consent process will typically take place in the emergency room, prior to surgical fixation of their open fracture. To discuss their participation, a member of the study team will approach potentially eligible patients.

To obtain informed consent, study personnel should follow the below procedures:

- Present study information in a manner that is understandable to the potential participant.
- Discuss the study with the potential participant and answer any questions he or she asks.
- Allow the potential participant an opportunity to discuss participation with their family, friends, or family physician, if desired.
- Confirm that the participant understands the risks and benefits of participating in the study and that their participation is voluntary.
- Complete and obtain signatures for informed consent form and obtain contact information from the participant.

The process of obtaining and documenting informed consent forms will be completed in accordance with local Good Clinical Practice recommendations.

Upon providing informed consent, study participants will be followed for 12 months from their fracture. Given the short follow-up time, the need for a regular reassessment of consent will not apply; however, participants may withdraw their consent at any time.

7.3 Confidentiality

Information about study participants will be kept confidential and will be managed in accordance with the below rules:

- All study-related information will be stored securely.
- All CRFs will be identified only by a coded participant number and initials.
- All databases will be password protected.

In the event that a participant revokes authorization to collect or use personal health information, the clinical site retains the ability to use all information collected prior to the revocation of participant authorization. For participants who have revoked authorization to collect or use personal health information, attempts should be made to obtain permission to collect at least vital status (i.e., primary outcome data) at the end of their scheduled study period.

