Diagnosis and Main Inclusion Criteria	All patients 18 years of age or older who present to Muhimbili Orthopaedic Institute (MOI) for treatment of Gustilo-Anderson (GA) Type I, II or IIIA open tibia fractures will be screened for participation. Eligible patients must present to the hospital within 48 hours of their injury and receive surgical debridement of their open fracture wound within 7 days of their injury. The open wound must be primarily closable at the index debridement.
Treatment Groups	The pGO-Tibia trial will compare two solutions: 1) aqueous gentamicin solution (2mg/mL) in normal saline, or 2) normal saline only. A minimum of 5mL and a maximum of 40 mL of either solution will be injected into the fracture site immediately following primary closure of the traumatic wound.

Randomization	Allocation to the study groups will be performed using a web-based randomization. The randomization sequence was generated using randomly permuted blocks of 4, 6, and 8 with a 1:1 allocation ratio.
Study Outcomes	The definitive trial primary outcome is occurrence of FRI. Secondary outcomes of the definitive trial are the occurrence of 1) nonunion, and 2) unplanned fracture-related reoperation within 12 months of definitive fixation. Definitive trial subsidiary outcomes include health-related quality of life, radiographic healing, and clinical healing. A blinded adjudication process will judge each study event on occurrence of FRIs, nonunions, and unplanned fracture-related reoperations.
Feasibility Outcomes	This pilot trial will focus on the following feasibility endpoints: Recruitment: number of patients screened, number and proportion of patients screened that are eligible, enrolled, randomized, and receive intervention. Retention: number and proportion of randomized patients who attend each follow-up visit. Data collection completeness, solution quality control, masking and concealment, and evaluation of primary and secondary outcomes (reliability of fracture-related infection and mRUST scoring, radiographic image quality, and completeness of EQ-5D and FIX-IT).
Follow-Up	Study participants will be followed at 2 weeks, 6 weeks, 3 months, 6 months, 9 months, and 12 months from their fracture.
Sample Size	50 individuals per arm will be included in the feasibility trial.

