2.0 STUDY AIMS AND HYPOTHESES

The study described herein is a single-center pilot trial to evaluate the feasibility of necessary protocols including, recruitment, retention, masking and concealment, intervention, and follow-up. The described pilot study will establish effect sizes for appropriate power calculations for a subsequent definitive trial.

The overarching objective of the definitive trial is to test whether injection of intraoperative local gentamicin impacts the rate of fracture-related infection following GA Type I, II or IIIA open tibia fractures in Tanzania. We hypothesize that the risk of fracture-related infection will be reduced by the intraoperative use of locally administered gentamicin at the time of wound closure.

2.1 Definitive Trial Specific Aims:

1. Compare the rate of fracture-related infection at one year after intraoperative local gentamicin injection or intraoperative local saline injection among adults treated operatively for GA Type I, II, or IIIA open tibia fractures. [Primary aim]
2. Compare the occurrence of 1) nonunion, and 2) unplanned fracture-related reoperation after intraoperative local gentamicin injection or intraoperative local saline injection among adults treated operatively for GA Type I, II, or IIIA open tibia fractures. [Secondary aims]
3. Evaluate the economic impact of fracture-related infection (FRI) after open tibia fractures in Sub-Saharan Africa including direct medical costs and lost productivity. [Secondary aims]

Null hypothesis: There is no difference in the rate of fracture-related infection between local gentamicin administration and saline administration for adult patients with GA Type I, II, or IIIA open tibia fractures treated in Sub-Saharan Africa.

Alternative hypothesis: Intraoperative local gentamicin administration decreases the occurrence of fracture-related infection in adult patients with GA Type I, II, or IIIA open tibia fractures treated in Sub-Saharan Africa.

2.2 Feasibility Trial Specific Aims:

Outcomes include rates of screening, enrollment, randomization, allocation, reliability of intervention, subject retention, and data completeness.

Specifically, feasibility outcomes are:

1. Recruitment: number of patients screened, number and proportion of patients screened that are eligible, enrolled, randomized, and receive intervention.

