2. Retention: number and proportion of randomized patients who attend each follow-up visit. We aim for an adherence rate at follow-up of 80% at one year.
3. Data collection completeness: proportion of fracture-related infection criteria, EuroQol-5 Dimensions, 3-level questionnaire (EQ-5D), Function Index for Trauma (FIX-IT), and Modified Radiographic Union Score for Tibia (mRUST)¹⁷ indices complete at each time point.
4. Solution quality control: confirmation of the ongoing sensitivity of standard organisms to trial solutions via interval testing.
5. Masking and concealment: determination of the continued masking of surgeons to solution identity via intraoperative surgeon survey.
6. Evaluation of primary and secondary outcomes: reliability of fracture-related infection and mRUST scoring¹⁷, radiographic image quality, and completeness of EQ-5D and FIX-IT.

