4.7.2 Definitive Trial Outcomes

Primary Outcome

The primary outcome is occurrence of *fracture-related infection* (FRI) a binary variable. FRI diagnosis is likely to peak between 3 and 6 months after surgery and has a non-normal time-to-event distribution, with incident cases rarely presenting later than 12 months after surgery. Any of the four following diagnostic criteria are confirmatory for infection: (1) fistula, sinus or wound breakdown; (2) purulent drainage from the wound or presence of pus during surgery; (3) phenotypically indistinguishable pathogens identified by culture from at least two separate deep tissue/implant specimens; or (4) presence of microorganisms in deep tissue taken during an operative intervention, as seen on histopathological examination.

Secondary Outcomes

The following secondary outcomes will be assessed:

1. Occurrence of nonunion, a binary variable, as defined by:
 - a. Any unplanned reoperation for promotion of bone healing; OR
 - b. mRUST ≤ 10 AND either: FIX-IT score ≤ 11 at 12 month follow-up, OR recommendation by treating surgeon for nonunion repair surgery.
2. Occurrence of unplanned fracture-related reoperation, a binary variable, for infection, wound healing, or fracture union, excluding removal of implants for prominence/irritation. This may include but is not limited to:
 - a. Irrigation and debridement of surgical incisions or open fracture wounds due to infections or wound healing problems;
 - b. Revision wound closure for dehiscence;
 - c. Soft tissue coverage procedure for infected or necrotic wound;
 - d. Fracture delayed union or nonunion surgery (such as bone grafting or implant exchange);

- e. Reoperation for hardware or prosthesis failure due to infection or bone-healing problems;
- f. Amputation for infection, wound or fracture healing problem.

Subsidiary Outcomes

The following subsidiary outcomes will be assessed:

1. Radiographic healing via the mRUST score, an ordinal scale ranging from 4 to 16.
2. Clinical healing via the FIX-IT score, an ordinal scale from 0-12 that encompasses two domains, ability to weight-bear and pain at fracture site, each scored from 0-6: ability to weight-bear and pain at fracture site.
3. Health-related quality of life via EQ-5D.
4. FRI suggestive criteria, including clinical (wound redness, fever) and radiographic signs (sequestrum), elevated serum inflammatory markers, and new onset or increased wound drainage.

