4.7.3 Steering Committee and Adjudication

The Steering Committee (SC) for the study will consist of [name], [name], [name], [name], and [name] (principal trial statistician). The Steering committee will be responsible for performing adjudication review and approving any sub-projects, as outlined below.

Review of the following study events will require review from the members of the study steering committee:

1. Death of a patient
2. Surgical complications requiring reoperation

The review, comment, and voting process will occur on REDCAP. Three steering members will need to evaluate each event that is put up for review. The steering committee members are responsible for providing the following inputs for each event:

1. Comments/opinions/justifications
2. Vote (yes or no): question varies depending on the event
 - a. Death event: question not applicable
 - b. Surgical complications requiring reoperation: does the patient need a reoperation?
3. Vote (yes or no): is this event a primary outcome of the study?

Adjudication review will be conducted every 2 months.

Additionally, the steering committee will meet monthly to review standardized REDCap data quality reports.

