5.2.1 Primary pre-specified analysis

Outcome Variable: the occurrence of FRI, as a binary outcome. We will denote this by Y_i , for person i . For each individual, we also record the time under observation, T_i . This value will be censored at the end of the follow-up time. [17]

Primary Analysis: the primary analysis will be conducted as a binomial regression with the complementary log-log link. This allows the available person-time to be used.

The estimated effect will be the relative hazard.

The analysis will be two-sided, with a type I error rate (alpha) of 0.05. Because there is no intention of including patients from this pilot trial into a subsequent definitive study, each trial (pilot and definitive) is completely separate, with an independent alpha.

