Statistical considerations. Intent to treat analysis is recommended, but impossible when the primary outcome is missing. We will conduct exploratory regression of missingness, and observation time, using the following predictors: gender, severity of injury, distance to clinic, and age.

Secondary analyses. All secondary analyses will be sharply distinguished from the primary pre-specified analysis and will be identified as such. Secondary analyses include outcome variables or planned subsets, which contribute either additional insight or address different scientific questions than the primary analysis.

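### Section 7.3 labels vital status as primary outcome data for participants who revoke authorization, but the primary outcome is FRI; separately, the missingness regressions omit treatment arm

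*Combined protocol and SAP*

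**What the plan says.** **Revoked authorization.** Section 7.3 (Confidentiality) lets the site keep using everything collected before revocation. It then says attempts should be made to "obtain permission to collect at least vital status (i.e., primary outcome data") at the end of the scheduled study period.

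**The primary outcome.** The Study Summary states: "The definitive trial primary outcome is occurrence of FRI". Section 4.7.2 (Definitive Trial Outcomes) defines it: "Any of the four following diagnostic criteria are confirmatory for infection", followed by four clinical, surgical, culture and histology criteria. Section 5.2.1 carries the same variable into the analysis: "Outcome Variable: the occurrence of FRI, as a binary outcome", together with each person's time under observation.

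**Where death appears.** Section 4.7.3 sends deaths and complications requiring reoperation to the steering committee. For each event its members vote on a generic question: "is this event a primary outcome of the study". Section 7.5.2 lists death as a criterion for a serious adverse event.

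**What the pilot needs.** Section 2.2 lists as a feasibility outcome "Data collection completeness: proportion of fracture-related infection criteria", among other instruments. Section 2.0 adds: "The described pilot study will establish effect sizes for appropriate power calculations".

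**Missing data.** Section 5.2.2 (Statistical considerations) says intention-to-treat analysis is impossible where the primary outcome is missing. It plans exploratory regressions of missingness and of observation time "using the following predictors: gender, severity of injury, distance to clinic, and age".

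**The concern.** The parenthesis in 7.3 states an identity that is false in this trial, and it sits in an instruction to sites. A coordinator who takes it at face value will believe that a vital status check has secured the primary outcome. Keeping earlier data does not cover this. Section 4.7.2 expects FRI diagnoses to peak 3 to 6 months after surgery, with few after 12, so someone who revokes early may have most of the risk period still ahead. Later FRI status can then be had only by asking, with permission. What is at stake is completeness of FRI data, which the pilot itself sets out to measure.

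The second point is independent of the first. Regressions meant to describe who is lost, and when, should be able to show whether loss differs between the two arms being compared. With the listed predictors they cannot.

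**Working it through.** **Step 1: is vital status any listed outcome?** This is a comparison of text.

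| Level | Listed outcomes | Section | Death included? |
|---|---|---|---|
| Primary | FRI, by any of four criteria | Study Summary, 4.7.2, 5.2.1 | No |
| Secondary | Nonunion; unplanned fracture-related reoperation | Study Summary, 4.7.2 | No |
| Subsidiary | mRUST, FIX-IT, EQ-5D, FRI suggestive criteria, CRP, costs | 4.7.2 | No |
| Feasibility | Recruitment, retention, data completeness, solution quality control, masking, outcome evaluation | 2.2, 4.7.1 (Feasibility Trial Outcomes) | No |
| Table 2 outcomes footnote | FRI; unplanned fracture-related reoperation | 4.4 | No |

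Reading 'primary outcome' in 7.3 as the pilot's own endpoint does not rescue it, since death is not a feasibility outcome either. Knowing that a participant is alive meets none of the four FRI criteria and rules none out.

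**Step 2: scale in the pilot.** Inputs: 12% control infection rate and a 50% relative reduction, hence 6% (section 5.1); 50 per arm (Study Summary).

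These rates reproduce the plan's own sample size, which is not in dispute. With p̄ = 0.09, two-sided alpha 0.05 and power 0.80:

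- n per arm = [1.960 × √(2 × 0.09 × 0.91) + 0.842 × √(0.12 × 0.88 + 0.06 × 0.94)]² / 0.06² = 355.9, rounded up to 356.
- Total 712; 712 / 0.80 = 890, as stated.

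Expected pilot events are 50 × 0.12 = 6 and 50 × 0.06 = 3, so 9 in all. One FRI case recorded only as alive is 1/9 = 11% of expected events. For comparison, an observed 6/50 has an exact 95% confidence interval of 4.5% to 24.3%, so sampling error far exceeds the effect of one case.

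The expected number of revocations is not stated, so no total effect can be calculated. The 20% in 5.1 is general loss to follow-up and is not a revocation rate.

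**Step 3: the arm term.** Section 5.2.2 names four predictors: gender, injury severity, distance to clinic and age. None carries allocation, so the fitted models cannot estimate a difference in loss between arms. To see what an arm term could deliver in the pilot, assume overall loss of 20% in one arm and 30% in the other, with 50 per arm:

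- Standard error under no difference: √(2 × 0.25 × 0.75 / 50) = 0.0866.
- Standard error under the difference: √((0.20 × 0.80 + 0.30 × 0.70) / 50) = 0.0860.
- Power ≈ Φ[(0.10 − 1.96 × 0.0866) / 0.0860] = Φ(−0.81) ≈ 21%. An exact binomial sum also gives 21%.

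An arm term in the pilot is therefore descriptive and would not serve as a test.

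**The case against.** The strongest reply is that 7.3 says 'at least' and names primary outcome data. A site that looks up the primary outcome finds only FRI, so the sentence is self-contradictory but does not tell sites to stop at alive or dead. The clause reaches only people who revoke and then agree to be asked. Their earlier data are kept, and 5.2.1 uses available person-time, so they still contribute to the analysis. The regressions in 5.2.2 are exploratory, and 5.2 says the methods are given mainly for planning and will be revised after the pilot.

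Most of this stands, and it limits the size of the point. It does not remove the error: the wording permits a compliant site to hold no FRI status after revocation, and a site should not have to resolve the contradiction itself.

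Three stronger readings are tempting, and the documents do not support them:

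- *That the plan treats death as the primary outcome.* The vote in 4.7.3 is generic and also covers reoperations. It adds some ambiguity, but every definition says FRI.
- *That one lost FRI case would materially shift the definitive trial's sample size.* That requires dropping the revoker altogether, contrary to 7.3 and 5.2.1, and any shift would be trivial beside the interval in Step 2.
- *That the definitive trial's estimate will be biased by missing FRI.* Material bias in the relative hazard would need loss that depends on both FRI and arm. The masking described in 4.6 makes this less likely, and that trial's analysis plan is still to be detailed.

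**Conclusion.** The point holds at minor severity. Section 7.3 is wrong as written: it equates vital status with primary outcome data when the primary outcome is FRI and death is not a listed outcome at any level. Its effect is unquantified and probably small, because the number of revocations is not given and pre-revocation data and person-time are retained. The 11% figure describes one case at the planning rates and is not an estimate of expected harm; it assumes that the rates in 5.1 apply to the pilot.

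The omission of treatment arm in 5.2.2 is also real, but it is a separate refinement. Its value in the pilot is descriptive, given about 21% power for a difference of 20% versus 30% in loss.

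**What to change.** **Section 7.3.** Replace the parenthesis so that, with the participant's permission, sites seek FRI status, with date, at the end of the scheduled study period, and list vital status as a separate item. The five telephone FRI questions already described in 4.4 may be used. The text should note that their validation is itself a pilot outcome (4.7.1, Feasibility Trial Outcomes) and that they cannot supply the culture or histology criteria. If permission is refused, nothing further is collected.

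**Section 5.2.2.** Add treatment arm to the regressions of missingness and observation time and report it descriptively. It can be entered under the coded labels Solution A and Solution B, so analysts stay masked.

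**Cost.** One phrase and one predictor, with no new visits or instruments. Section 7.1 requires any protocol modification to go to both ethics boards, and 7.4 requires a formal amendment where a change to study procedures may affect conduct. Both edits can go in a single submission.
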